## 5.4 *CEM-guided biopsies:*

CEM- guided biopsy device uses a stereotactic technique to target areas of abnormal enhancement in the breast. The first commercially available CEM-guided biopsy device (GE Healthcare Serena BrightTM CEM biopsy system) has been U.S. Food & Drug Administration 510(k) cleared in May 2020. This system is capable of both conventional stereotactic and CEMguided biopsies. For both methods the system uses angular mammographic acquisitions in the breast to calculate the target, but for stereotactic biopsies it uses the morphologic abnormality in the breast as the target, whereas for CEM-guided biopsies it uses the area of suspicious enhancement as the target. With the exception of targeting, the biopsy procedure and the biopsy needles used for the procedure are identical for both methods (Appendix A).

For those study patients who demonstrate abnormal CEM enhancement with no correlate on FFDM or US, GE Healthcare Serena BrightTM CEM biopsy system will be used to perform CEM- guided biopsies. CEMguided biopsies may also be utilized for choosing the areas of most prominent CEM enhancement as biopsy targets for extensive mammographic abnormalities, where precise targeting is difficult. The presence of distinct abnormal enhancement within a target is expected to correlate with the most metabolically active areas of the lesion [31]. This may improve the accuracy of biopsy and decrease the rate of upgrade to malignancy at surgery.

5.5 Biopsy markers and post-procedure mammograms

For all biopsy methods a biopsy marker will be placed at the target as the standard of care [32]. As a part of the standard of care we will perform a post-procedure mammogram after tissue sampling and clip placement [32].

For those patients who undergo CEM-guided biopsies for pathologic enhancement, post-procedure CEM images of the biopsied breast will be obtained.

The technical success of CEM guided biopsies will be determined by the fraction of biopsies that achieve adequate sampling of the target.

### 5.6 Ground truth

Pathology results from image guided biopsies and surgical pathology results will be considered the ground truth. Breast tissue lesions will be categorized as positive if diagnosed as invasive BC or ductal carcinoma in situ (DCIS), and otherwise will be categorized as negative, including the lesions of uncertain malignant potential without subsequent surgical upgrade to invasive cancer or DCIS.

### 5.7 Pathology

As part of the standard of care, the biopsy will be evaluated by a breast pathology specialist as part of the routine diagnostic clinical service. After the case has been finalized, the slides will be reviewed by the breast pathology collaborator for this study in order to record the additional information listed below.

The following parameters will be recorded:

- Pathologic diagnosis
- The maximal diameter of the dominant abnormality
- The maximal diameter of the abnormality with the highest level of suspicion (Invasive cancer, in-situ cancer, atypia)

### *For invasive cancers/DCIS:*

- *Histologic/nuclear grade*
- Presence of tumor necrosis for invasive carcinoma and/or comedonecrosis for DCIS
- Architectural growth pattern for DCIS
- *The Presence of lymphovascular invasion*
- Biomarker status (ER, PR, Her-2/neu, Ki-67)
- Presence of calcifications
- *Tumor infiltrating lymphocyte analysis*

## 5.8 Multiple reader study design

Low-energy images produced as a part of CEM are of sufficient quality for clinical interpretation (equivalent to directly acquired 2D mammographic images), and will be interpreted accordingly by radiologists.

The reader study will have 2 components:

1. The first interpretation of the entire CEM study, including all its components, will be done clinically by one radiologist after the exam is performed. Its results will be actionable and will affect the patient's management.

2. Multiple reader study. The results of this study will not be used for clinical care, and will not be reported to the patients or referring clinicians.

Each patient's study will contain LE images (FFDM equivalent), DBT images, and CEM subtraction images. All these components will be separated and presented to radiologists in different combinations for within-subject comparison. As a part of the multi-reader component, the study images for every patient will be reviewed in 4 sets by 5 radiologists each. Images for the same patients will be read by radiologists with an interval of at least 2 month to prevent case memorization.

1. LE (FFDM equivalent) images only

2. LE (FFDM equivalent) with DBT

3. LE followed by DBT followed by CEM subtraction images

4. LE followed by subtraction images (complete CEM study)

The study radiologists will be aware of the patients' inclusion criteria, but will be blinded to the clinical diagnostic reports, any and all comparison images of any modality outside of the assigned protocol, and the pathology report.

5.9 The sequence of the imaging studies and the parameters to be collected are presented below. The reporting will be done using ACR BI-RADS Fifth edition recommendations.

### 1. LE images:

- Laterality
- Clock position
- 3 dimensional measurements of the index mass (antero-posterior, craniocaudal, transverse), when possible
- View demonstrating the finding best (CC, MLO, LM)
- The number, laterality, and clock position of additional lesions
- Breast density (Bi-RADS A-D)
- BI-RADS assessment per lesion using the 7-point BI-RADS® scale (1, 2, 3, 4a, 4b, 4c, 5) (Fig.3). BI-RADS categories 1-3 will be considered negative, and BI-RADS categories 4-5 will be considered positive.

2. DBT images:

- Laterality
- Clock position

- 3 dimensional measurements of the index mass in question (anteroposterior, craniocaudal, transverse), when possible
- View demonstrating the finding best (CC, MLO, LM)
- The number, laterality, and clock position of additional lesions
- BI-RADS assessment using the 7-point BI-RADS® scale (1, 2, 3, 4a, 4b, 4c, 5) (Fig.3). BI-RADS categories 1-3 will be considered negative, and BI-RADS categories 4-5 will be considered positive.

3. CEM

- Background enhancement
- The presence or absence of pathologic enhancement in the area of index mass, and the degree of enhancement above background.
- 3 dimensional diameters of the pathologic enhancement (anteroposterior, craniocaudal, transverse), when available.
- The number, laterality, and clock position of additional lesions
- View demonstrating the finding best (CC, MLO, LM)
- *BI-RADS assessment after adding CEM. BI-RADS categories 1- 3 will be considered negative, and BI-RADS categories 4-5 will be considered positive.*

| BI-RADS ® ASSESSMENT CATEGORIES |   |   |  |  |  |
|--|---|---|--|--|--|
| Category 0: Mammograpl
Ultrasound &     | hy: Incomplete – Nee
MRI: Incomplete – I | ed Additional Imaging Evaluation and/or Prior Mammograms for Comparison
Need Additional Imaging Evaluation |  |  |  |
| Category 1: Negative                       |   |   |  |  |  |
| Category 2: Benign                         |   |   |  |  |  |
| Category 3: Probably Benig                 | jn  |   |  |  |  |
| Category 4: Suspicious                     | Mammography                                 | Category 4A: Low suspicion for malignancy   |  |  |  |
|  | & Ultrasound:                               | Category 4B: Moderate suspicion for malignancy  |  |  |  |
|  |   | Category 4C: High suspicion for malignancy  |  |  |  |
| Category 5: Highly Suggest                 | tive of Malignancy                          |   |  |  |  |
| Category 6: Known Biopsy                   |   |   |  |  |  |

Fig. 3 BI-RADS assessment categories [1]

A PACS-based MDACC-created and approved software will be utilized for data collection by the radiologists and directly transferred for statistical analysis.

## Lexicon

There is currently no standard reporting language for contrast enhanced mammography. The most commonly used conventional approach to reporting will be utilized for the study: for the mammographic findings, the BI-RADS mammography lexicon will be utilized; for the enhancement patterns, the BI-RADS MRI lexicon will be applied (fig.4) [1, 33].

| لگ                                  |   | MAGNETIC RESC   | NANCE IMAGI                    | ١G  |                                |
|-------------------------------------|---|---|--------------------------------|---|--------------------------------|
| Amount of                           | a Almost entire   | a. Almost entirely fat  |                                | Nipple retraction                                 |                                |
| fibroglandular                      |   | 
 
Almost entirely fat
 
b. Scattered fibroglandular tissue
 
 |                                | Nipple invasion                                   |                                |
| tissue (FGT)                        |   | us fibroglandular tissue  |                                | Skin retraction                                   |                                |
|                                     | d. Extreme fibro  | d. Extreme fibroglandular tissue  |                                | Skin thickening                                   |                                |
| Background                          | Level   | Minimal   | 1                              | Skin invasion                                     | Direct invasion                |
| parenchymal
enhancement
(BPE) | Level .   | Mild  |                                |   | Inflammatory cancer            |
|                                     | Competition of  | Moderate
Marked  |                                | Avillan: advacath                                 |                                |
|                                     |   |   |                                | Axillary adenopathy                               |                                |
|                                     |   |   |                                | Pectoralis muscle invasion
Chest wall invasion |                                |
|                                     | Symmetric or Symmetric
asymmetric Asymmetric           |   |                                | Chest wall invasion
Architectural distortion   |                                |
| Focus                               | asymmetric  | Asymmetric  | Fat containing lesions         | Lymph nodes                                       | Normal                         |
|                                     |   |   | rat containing lesions         | Lympn nodes                                       |                                |
| Masses                              | Shape   | Oval  |                                |   | Abnormal                       |
|                                     |   | Round   | Fat necrosis                   |   |                                |
|                                     |   | Irregular   | 1                              | Hamartoma   |                                |
|                                     | Margin  | Circumscribed   |                                | Postoperative seron                               | na/hematoma with fat           |
|                                     |   | Not circumscribed   | Location of lesion             | Location  |                                |
|                                     |   | - Irregular   |                                | Depth   |                                |
|                                     |   | - Spiculated  | Kinetic curve                  | Initial phase                                     | Slow                           |
|                                     | Internal  | Homogeneous   | assessment                     |   | Medium                         |
|                                     | enhancement   | Heterogeneous   | Signal intensity               |   | Fast                           |
|                                     | characteristics   | Rim enhancement   | (SI)/time curve
description | Delayed phase                                     | Persistent                     |
|                                     |   |   | description                    | Delayed phase                                     | Plateau                        |
|                                     |   | Dark internal septations  |                                |   |                                |
| Non-mass                            | Distribution  |   | Implants                       | Implant material an                               | Washout                        |
| Non-mass
enhancement             | Distribution  | Focal   | Implants                       | Implant material and
lumen type                | d Saline                       |
| (NME)                               |   | Linear  |                                | rumen type  | Silicone                       |
| ()                                  |   | Segmental   |                                |   | - Intact                       |
|                                     |   | Regional  |                                |   | - Ruptured                     |
|                                     |   | Multiple regions  | 1                              |   | Other implant material         |
|                                     |   | Diffuse   |                                |   | Lumen type                     |
|                                     |   |   |                                |   | - Single                       |
|                                     |   |   |                                |   | - Double                       |
|                                     |   |   | 4                              |   | - Other                        |
|                                     | Internal  | Homogeneous   |                                | Implant location                                  | Retroglandular                 |
|                                     | enhancement
patterns                                   | Heterogeneous   |                                |   | Retropectoral                  |
|                                     | patterns  | Clumped   |                                | Abnormal implant                                  | Focal bulge                    |
|                                     |   | Clustered ring  |                                | contour   |                                |
| Intramammary lym                    | ph node   |   | ]                              | Intracapsular silicor                             | e Radial folds                 |
| Skin lesion                         |   |   | ]                              | findings  | Subcapsular line               |
| Non-enhancing
findings           | Ductal precontrast high signal on T1W                     |   | 1                              |   | Keyhole sign (teardrop, noose) |
|                                     | Cyst  |   | 1                              |   | Linguine sign                  |
|                                     | Postoperative collections
(hematoma/seroma)            |   |                                | Extracapsular
silicone                         | Breast                         |
|                                     | Post-therapy skin thickening and
trabecular thickening |   |                                | Water droplets                                    | Lymph nodes                    |
|                                     | Non-enhancing mass  |   |                                | Peri-implant fluid                                |                                |
|                                     | Architectural distortion                                  |   | 1                              |   |                                |
|                                     | Signal unid from  | foreign bodies, clips, etc.   | 1                              |   |                                |

Fig. 4 MRI descriptors of the BI-RADS lexicon [34]

#### Follow-up

We will follow up the study patients for at least 12 months. We will review the patients' medical records, including clinical notes, pathology, and radiology reports. This will be done to monitor for possible development of new BC or cancer recurrence. Results from biopsy and/or follow-up will serve as the ground truth and will be used to determine the true positive and true negative.

## 6.0 Data and Specimen Banking\*

6.1 Registration

All subjects who have given informed consent and meet eligibility criteria must be registered through the MDACC CORe system.

### 6.2 Questionnaire

If not already enrolled in the MERIT study (PA17-0584), participants will be asked to complete a questionnaire that collects data on personal and family history of cancer, health status, breast cancer risk factors, diet, weight gain, and physical activity (Appendix C1, C2). The questionnaire or a link to the questionnaire may also be sent to the participants at a different time from their mammography appointment (before or after) via text or email, or through our electronic health record system. The questionnaire data may also be collected via telephone by research staff. Essential data elements will be collected from the patients' medical records.

### 6.3 Biospecimen Collection

A member of the research staff will collect blood at the time of the CEM examination but before contrast is injected. To collect blood specimens, a  $PIVO^{TM}$  device (Velano Vascular) may be used by trained staff to perform the blood draw and the contrast injection through the same IV access to avoid multiple patient sticks (Appendix D).

The blood will be delivered to a facility within MD Anderson where it will be processed by trained personnel. Additional details regarding blood processing Standard Operating Procedures (SOPs) are described in Appendix E. The McCombs Institute will manage the biospecimens and will utilize portions of samples to evaluate candidate biomarkers.

Samples from each patient will be assigned a unique specimen identification number. This number will become a part of the repository and will be used to identify the subjects' data in the system. In this way, no personal identification information such as name or a social security number is necessary.

If the participant is also enrolled in any other McCombs Institute early detection study (for example, 2013-0609, PA17-0791), biospecimen collection is not required if the last collection was within 30 days.

## 7.0 Sharing of Results with Subjects\*

- 7.1 The results of the first clinical read of CEM studies will be provided within the frame of the clinical workflow, will affect patient care, and will be reported to the patient and her referring physician.
- 7.2 The results of the multi-reader component will not be shared with the patient or her referring provider.

# 8.0 Study Timelines\*

- 8.1 Describe:
  - The subject participation will consist of a one-time CEM study. The patients' pertinent clinical information, including imaging, pathology and clinical reports will be collected for 12 months.
  - In those patients who need a CEM-guided biopsy, the participation in the study will also include IV contrast administration for the biopsy.
  - The study enrollment process is expected to continue for 12 months.
  - March 2022

## 9.0 Inclusion and Exclusion Criteria\*

- 9.1 INCLUSION CRITERIA
  - Female patients 18 years of age or older with known invasive or in-situ BC diagnosed at an outside facility and presenting to MD Anderson for staging with imaging.
  - Female patients 18 years of age or older referred from outside institutions with imaging findings categorized as highly suspicious (BI-RADS 5 or 4C) on outside imaging or on rereview by MD Anderson's radiologists and referred for staging at MDACC.
  - Willingness to participate in the study and ability to provide informed consent.
- 9.2 EXCLUSION CRITERIA
  - •

•

- Breast surgery within 6 months.
- *Known allergy to iodine-containing contrast agents.*
- *History of anaphylactic reaction to any substance that required hospitalization or IV placement.*
- *Renal insufficiency; hyperthyroidism.*
- Detection of non-breast primary or metastatic cancer in the breast.

## 9.3 PROCEDURE TO OBTAIN CONSENT

Eligible and interested subjects will be consented for study participation. A research staff member who is trained in the informed consent process will explain the study, invite the patients to enroll, and obtain the informed consent of women who wish to participate. Subjects may be enrolled using the approved MD Anderson procedures for remote consenting.

## **10.0** Local Number of Subjects

10.1 83 subjects

# **11.0 Recruitment Methods**

Research staff will identify potential subjects via the UT MDACC information system. The patients will be approached by either the Clinical Cancer Prevention or the Diagnostic Imaging faculty, or qualified research staff, for their consent prior to their procedure. This may be done before or on the day of their diagnostic mammography appointment at the MDACC Nellie B. Connally Breast Imaging Center, or via a telephone conversation or a teleconference with a study coordinator, an email, or text messaging via MD Anderson approved systems. MyMDAnderson website and flyers may be utilized to contact patients. The patients will not be compensated for their participation.

# 12.0 Withdrawal of Subjects\*

*12.1* The patients may refuse participation at any time for any reason.

12.2 The subjects will be withdrawn from the research without their consent in the following situations:

- The patient has consented to the study but is determined to be ineligible before CEM is completed
- The patient does not complete CEM imaging
- The patient refuses a biopsy or chooses to have a biopsy at an outside *institution*
- In these cases, the patients' research files will be removed and any collected data will not be used for analysis.

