## 2.2 Secondary Objectives

- To evaluate the sensitivity, specificity, positive and negative predictive value of CEM compared to LE CEM images (FFDM equivalent), DBT and ultrasound for the detection of additional malignant lesions in the ipsilateral and contralateral breast.
- To evaluate the difference of the index cancer size estimation among CEM, LE images, DBT, and ultrasound compared to pathology measurements as the ground truth.
- To evaluate the incremental cancer detection rate provided by CEM, DBT, and US compared to the OSF diagnosis.
- 2.3 Exploratory Objectives
  - To evaluate the rate of referral to breast MRI in the study cohort.
  - To evaluate the performance of MRI for breast cancer diagnosis and compare it with other imaging modalities of CEM, LE images, DBT and ultrasound.
  - To evaluate the feasibility of CEM-guided biopsy of CEMonly detected lesions. The technical success of CEM guided biopsies will be determined by the fraction of biopsies that achieve adequate sampling of the target.

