# 4.0 Study Endpoints\*

4.1 Primary study endpoint:

Accuracy of CEM for incremental cancer detection in the ipsilateral and contralateral breasts. For the purpose of the study, up to 4 additional biopsy sites will be included in the analysis.

[figure not shown]
- 4.2 Secondary study endpoints:
  - Sensitivity, specificity, positive and negative predictive value of CEM, LE images, DBT, and ultrasound compared to pathology measurements as the ground truth.
  - The difference of the largest measurement of the index cancer on *LE*, *CEM*, *DBT* and *US* compared to pathology.
  - Incremental cancer detection rate provided by CEM, DBT and US.
- 4.3 Exploratory Endpoints:
  - *Rate of breast MRI utilization and the corresponding diagnosis in the study cohort.*
  - *The fraction of CEM biopsies that achieve adequate sampling of the target.*

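### Section 12.2 drops every result of a patient who refuses a biopsy or has one elsewhere, although the analysis is per lesion and other sources of truth may exist

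*Combined protocol and SAP*

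**What the plan says.** Section 12.2 lists situations in which a subject is withdrawn without her consent. One is "The patient refuses a biopsy or chooses to have a biopsy at an outside" institution. The last bullet says that in these cases the patient's "research files will be removed and any collected data will not be used for analysis". Withdrawal at the patient's own wish is dealt with separately, in 12.1.

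Other sections bear on this rule:

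- **Unit of analysis.** Section 4.1 says "up to 4 additional biopsy sites will be included in the analysis". Section 15.2 sizes the study with an average of 1.4 lesions per patient and a variance of 1, and section 15.3 plans methods for multiple lesions.
- **Reference standard.** Section 5.6 says "Pathology results from image guided biopsies and surgical pathology results will be considered the ground truth" and names no institution; section 15.1 also relies on pathology. The Follow-up subsection at the end of section 5 says "Results from biopsy and/or follow-up will serve as the ground truth".
- **Records.** That subsection plans review of "medical records, including clinical notes, pathology, and radiology reports" for at least 12 months. Section 8.1 says "pertinent clinical information, including imaging, pathology and clinical reports will be collected for 12 months".
- **Index-cancer size.** A secondary objective in section 2.2 is "To evaluate the difference of the index cancer size estimation among CEM, LE images, DBT, and ultrasound compared to pathology" measurements.
- **Entry.** Section 9.1 admits patients whose cancer was diagnosed at an outside facility.

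**The concern.** The removal rule works per patient, while the endpoint works per lesion. Section 12.2 does not say whether *a biopsy* means any one recommended biopsy or all of them. Literally it means any one. A woman with three additional sites who accepts two biopsies and declines the third then loses the two verified sites and her index-size measurements as well.

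On any reading, the rule discards a site whose truth becomes available later: from surgery, from an outside report that can be obtained, or from follow-up if the Follow-up subsection governs. The patient has gone before those sources can be used.

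The timing also matters. The first clinical CEM read is actionable (section 5.8), and section 13.3 says that CEM may show abnormalities needing biopsy. A CEM finding can thus create the recommendation whose refusal removes the patient. This is exclusion after the test in a paired accuracy study. If refusal is decided site by site, women with several sites are removed more often than women with one. The plan does not ask for removed patients or lesions to be counted, so a reader could not judge the effect.

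**Working it through.** **Inputs.** From section 15.2: 83 patients, 80% power, two-sided 0.05, accuracy difference 0.12, discordance 0.20, lesions per patient with mean 1.4 and variance 1, intracluster correlations 0.4 and 0.2. The documents give no refusal or outside-biopsy rate, so 2%, 5% and 10% are assumed.

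**1. The plan's own figure.** Lesion pairs = (1.960·√0.20 + 0.842·√(0.20 − 0.12²))² / 0.12² = 106.6. Patients = (106.6/1.4)·[1 + ((1 + 1.4²)/1.4 − 1)·ρ]. With ρ = 0.4 × 0.2 = 0.08 this is 82.9, so 83 is reproduced. The match depends on combining the two correlations in this way. In the same formula ρ = 0, 0.2 and 0.4 give 77, 94 and 111. Section 10.1 also gives 83, so there is no allowance for withdrawals.

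**2. Lesions.** 83 × 1.4 = 116.2.

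**3. Further lesions lost through refusal, if one refusal removes the patient.** Section 15.2 does not say whether the index lesion is counted, so two maximum-entropy distributions with mean 1.4 and variance 1 are used: on 0–4 sites (0.200, 0.360, 0.302, 0.117, 0.021) and on 1–5 sites (0.814, 0.089, 0.027, 0.022, 0.048). Refusal is beta-binomial with per-site rate r and within-patient correlation c. Lesions lost beyond the refused ones = 83·Σ p(N)·N·P(removed | N) − 116.2r. Results for 0–4 / 1–5:

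| r | c = 0 | c = 0.4 | c = 1 (one decision for all sites) |
|---|---|---|---|
| 2% | 2.5 / 2.5 | 1.4 / 1.1 | 0 / 0 |
| 5% | 6.0 / 5.8 | 3.3 / 2.7 | 0 / 0 |
| 10% | 11.2 / 10.4 | 6.2 / 5.0 | 0 / 0 |

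The 1–5 column lets the index biopsy be refused. If only additional sites can be refused, there are 83 × (1.4 − 1) = 33.2 of them, and at r = 5% the further additional lesions lost are 2.9, 1.4 and 0.

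**4. Who is removed, r = 5%.**

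| Sites | c = 0 | c = 0.4 | c = 1 |
|---|---|---|---|
| 1 | 5.0% | 5.0% | 5% |
| 2 | 9.8% | 7.9% | 5% |
| 3 | 14.3% | 9.8% | 5% |
| 4 | 18.5% | 11.3% | 5% |

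**5. Index-size data, r = 5%.** Patients removed = 83·Σ p(N)·P(removed | N) = 5.7 / 5.7 (c = 0), 4.6 / 4.9 (c = 0.4), 3.3 / 4.2 (c = 1). If only additional sites can be refused, the figures are 1.6, 1.2 and 0.8. The range is about 1 to 6 of 83.

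**6. Outside biopsy.** If a share q of patients choose one, regardless of number of sites, 83q = 1.7, 4.2, 8.3 patients and 116.2q = 2.3, 5.8, 11.6 lesions are removed at q = 2%, 5%, 10%. If half of the reports can be obtained, half of that is recoverable.

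**7. Power.** Scaling from the stated 80%, Φ(2.802·√(n/83) − 1.960) gives 0.780 at n = 79 (5% of patients removed) and 0.759 at n = 75 (10%). With ρ = 0.08, independent refusals at 5% per site and the 0–4 distribution, dropping only the refused lesions keeps 110 lesions and 78% power; dropping whole patients keeps 104 and 76%. At 10% per site the same comparison is 105 lesions and 76% against 93 and 71%.

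**The case against.** Part of the rule can be defended. Section 5.7 plans review of the slides by the study's breast pathology collaborator, and no section says that outside biopsy results will be accepted for additional lesions. Leaving them out protects a uniform reference. Surgery need not sample a refused site, for example one in the other breast. Many patients arrive with a tissue diagnosis, so the index lesion may seldom be at risk of refusal. The comparison is paired, so a removed patient leaves both the CEM and the LE results. Keeping data of withdrawn patients also depends on consent wording that is not in the reviewed text.

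These points limit the size of the problem and make the use of outside pathology an inference. They do not explain why other verified lesions and index-size data should be discarded for women who have not withdrawn under 12.1.

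Four stronger readings are tempting, and the documents do not support them:

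- **That 12.2 contradicts section 5.6 or the Follow-up subsection.** Those define truth for patients who are analysed; 12.2 decides who is analysed. The unsettled matter is between 5.6 and 15.1 (pathology) and the Follow-up subsection (biopsy and/or follow-up).
- **That the rule favours CEM.** Nothing links removal to CEM-LE discordance, so no direction can be derived.
- **That every refused site is lost because of 12.2.** Some may have no reference result in any case. The opposite claim, that a site without pathology is always unverified, also fails, because follow-up may count.
- **That the study becomes seriously underpowered.** Step 7 does not show this for removal of 5% to 10% of patients.

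**Conclusion.** The point holds as a matter of wording: 12.2 discards usable, verified data by rule, on an event after imaging that the CEM read can trigger, and the plan does not ask for the exclusions to be counted. Selection bias is possible but not shown.

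The size rests wholly on assumed rates. The refusal figures also require that one refusal is enough to remove the patient. At 5% per site the extra loss is 0 to 6 lesions of 116, depending on within-patient correlation and on whether the index lesion is at risk; it is nil if refusal is one decision for all additional sites. The power effect is minor at 5% to 10% of patients removed. High confidence covers the wording of 12.2 only. The change is worth making because it is cheap and keeps valid data, not because a large effect has been shown.

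**What to change.** Amend the last bullet of 12.2 so that:

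- (a) eligible patients with a completed CEM who have not withdrawn under 12.1 stay in the analysis, with all lesions that have a reference result and with their index-size data;
- (b) surgical pathology is accepted as reference, as is outside biopsy pathology where the report can be obtained, with a sensitivity analysis that leaves out outside results lacking the slide review of section 5.7;
- (c) only the refused site without a reference result is treated as missing, with best-case and worst-case bounds as a sensitivity analysis. Sections 5.6 and 15.1 and the Follow-up subsection must first be reconciled on whether follow-up counts as truth. The reference standard for other lesions does not change;
- (d) excluded patients and lesions are reported with reasons.

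The cost is a protocol amendment of a few sentences, requests for outside reports (some of which may not be obtainable), and a less uniform pathology review. The consent wording must agree with keeping these data and may need revision.
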